Appendix 9. Prohibited Concomitant Medications Which May Result in Drug-Drug Interaction (DDI)

This is not an all-inclusive list. Study personnel should stay current and consult with their pharmacy to exclude all concomitant medications that are CYP3A4/5 inhibitors or inducers.

Drug Category	Drugs or Supplement	Required Washout Period
Drug Guergery	a supplement	Requirement
CYP3A4/3A5	VIEKIRA PAK	10 days
Inhibitor	Anti-HIV retroviral drugs	or
	containing ritonavir	5 half-lives
	ritonavir	whichever is longer
	cobicistat	
	troleandomycin	
	telaprevir	
	itraconazole	
	indinavir	
	voriconazole	
	mifepristone	
	mibefradil	
	clarithromycin	
	posaconazole	
	telithromycin	
	grapefruit juice	
	ceritinib	
	conivaptan	
	nefazodone	
	nelfinavir	
	saquinavir	
	ribociclib	
	idelalisib	
	boceprevir	
	Erythromycin	
	Fluconazole	
	Atazanavir	
	Darunavir	
	Duvelisib	
	Diltiazem	
	Dronedarone	
	Crizotinib	
	Fedratinib	
	Letermovir	
	Aprepitant	
	Lefamulin	
	Casopitant	
	Amprenavir	
	Faldaprevir	
	Imatinib	
	Verapamil	

Drug Category	Drugs or Supplement	Required Washout Period
		Requirement
	Ravuconazole	
	Netupitant	
	Nilotinib	
	Istradefylline	
	Tofisopam	
	Cyclosporine	
	Ciprofloxacin	
	Voxelotor	
	Isavuconazole	
	Cimetidine	
	fluvoxamine	
CYP3A4/3A5	carbamazepine	10 days
Inducer	enzalutamide	or
	rifampicin	5 half-lives
	mitotane	whichever is longer
	avasimibe	
	rifapentine	
	apalutamide	
	ivosidenib	
	phenytoin	
	St John's Wort extract	
	phenobarbital	
	semagacestat	
	efavirenz	
	dabrafenib	
	cenobamate	
	lesinurad	
	bosentan	
	thioridazine	
	rifabutin	
	Lorlatinib	
	Nafcillin	
	talviraline	
	lopinavir modafinil	
	etravirine	
	elagolix	
	lersivirine	
	telotristat ethyl	
	terourstat euryr	

Note 1: Half-life refers to the half-life of the parent drug and its metabolites, which are inhibitors or inducers. The longest half-life should be used to calculate the period necessary to washout a medication prior to the first dose of study treatment.

Appendix 10. Additional Clinical Safety Data

The data below are from the Part 1A of the Study C3881001 clinical database as of 19 Jun 2020. These data are preliminary and may change. At that time 27 subjects were reported to have been screened and 20 subjects were shown to have been enrolled. The tumor types enrolled were prostate cancer (11 subjects), pancreatic cancer (3 subjects), colon cancer/colorectal cancer (2 subjects), squamous cell head and neck cancer/squamous cell tongue cancer (2 subjects), breast cancer (1 subject), and mesothelioma (1 subject). One subject each was enrolled in the 20, 40, 80 and 150 mg BID accelerated titration cohorts. Six subjects in the 250 mg BID cohort and 3 patients in the 375 BID mg cohort were enrolled prior to a partial clinical hold implemented in July 2019 when 2 subjects experienced Grade 3 events of hepatic hemorrhage (250 mg BID cohort) and intracranial tumor hemorrhage (375 mg BID cohort). Two additional subjects (1 each) with epistaxis and oral hemorrhage were also reported. Subsequently, study entry criteria were modified to reduce the risks of bleeding in a protocol amendment. As of the 19 Jun 2020 database version, no additional AEs of bleeding episodes have been reported.

One hundred and nineteen AEs were reported in 20 patients. Of the 119 AEs,

- Ninety-one AEs were either Grade 1 or 2 in 17 patients.
- The most frequency reported AEs (≥3 subjects) were nausea or worsening nausea (5 subjects), cough (4 subjects), anorexia (4 subjects), nasal drainage or congestion (4 subjects), nasal congestion or intermittent nasal congestion (4 subjects), abdominal pain, or abdominal/right upper quadrant (RUQ) pain (3 subjects), vomiting (3), anemia, or intermittent anemia (3 subjects), dyspnea (3 subjects), fatigue, or worsening fatigue (3 subjects) and headache (3 subjects). Twenty-five Grade 3 AEs were reported in 14 patients.
 - 3 AEs (anemia, intracranial tumor hemorrhage, and intrahepatic hemorrhage, each in 1 patient) were reported as attributed to PF-06952229 by the investigators. Of note, no additional hemorrhagic events have been reported following the modifications made to study entry criteria.
 - O 21 Grade 3 AEs considered unrelated to PF-06952229 were reported in 13 patients: 3 events of abdominal/abdominal RUQ pain, 2 events of hyponatremia, 2 events of anemia/worsening anemia, 2 events of constipation, 2 events of nausea, vomiting and dehydration, and 1 episode each of pneumonia, pulmonary embolism, musculoskeletal weakness left side, left hip pain, hyperbilirubinemia, hyperglycemia, increased ALT, increased AST, hypotension, and dysphagia.
 - o 1 Grade 3 AE (fatigue) was reported and the relationship to PF-06952229 has not been reported.
- Two Grade 4 AEs (sepsis and acute respiratory failure) were reported in 2 patients; both of which were deemed to be unrelated to PF-06952229.

• One Grade 5 AE was reported due to death due to tumor progression.

Serious AEs of intracranial tumor hemorrhage, intrahepatic hemorrhage, and anemia reported in 1 patient each were considered related to PF-06952229 by the investigators. Serious AEs not related to PF-06952229 were death due to tumor progression, oral hemorrhage, acute respiratory failure, sepsis, abdominal pain, pneumonia, anemia, hyponatremia, constipation, pulmonary embolism, left hip pain, and nausea/vomiting/dehydration. Each serious, unrelated AE was reported for 1 patient each.

1. VERSION HISTORY

Version	Section	Update
Amendment 1	All	Texts taken directly from the protocol are made italicized Updated per Protocol Amendment 3

2. INTRODUCTION

This analysis plan is meant to supplement the C3881001 study protocol. In this document, any text taken directly from the protocol is italicized. Any deviations from this analysis plan will be described in the Clinical Study Report (CSR). This SAP is based on Protocol Amendment 3 dated May 7, 2021.

2.1. Study Objectives

Part 1A

Primary Objectives

- *To assess safety and tolerability at increasing dose levels of PF 06952229 in patients with advanced/metastatic tumors*
- *To determine MTD and RP2D of PF 06952229 as a single agent.*

Secondary Objectives

- *To evaluate the single and multiple dose PK of PF 06952229 when given as a single agent.*
- *To evaluate preliminary anti tumor activity of PF 06952229 when given as a single agent.*
- *To evaluate preliminary biochemical responses as a measure of anti tumor activity of PF 06952229.*

CCI [REDACTED]

[REDACTED]

[REDACTED]

[REDACTED]

CC1

CC2

Part 1B

Primary Objectives

- *To assess safety and tolerability at increasing dose levels of PF 06952229 in combination with enzalutamide in patients with mCRPC.*
- *To determine MTD and RP2D of PF 06952229 in combination with enzalutamide in patients with mCRPC.*

Secondary Objectives

- *To evaluate the single and multiple dose PK of PF 06952229 when given in combination with enzalutamide.*
- *To evaluate preliminary anti tumor activity of PF 06952229 when given in combination with enzalutamide.*
- *To evaluate preliminary biochemical responses as a measure of anti tumor activity of PF 06952229 when given in combination with enzalutamide.*

CC1

CC2

CC3

CC4

CC5

Part 2A

Primary Objectives

- *To confirm safety and tolerability of PF 06952229 at the estimated RP2D in patients with mCRPC.*
- *To estimate efficacy of PF 06952229 at the estimated RP2D in patients with mCRPC.*
- *To confirm the RP2D of PF 06952229 as a single agent.*

Secondary Objectives

- *To estimate additional efficacy of PF 06952229 at the estimated RP2D in patients with mCRPC.*
- *To further evaluate the single and multiple dose PK of PF 06952229 when given as a single agent.*
- *To evaluate immune cells in paired pre and post treatment tumor biopsies (where available).*

CCI

Part 2B

Primary Objectives

- *To confirm PF 06952229 safety profile in combination with enzalutamide at the estimated RP2D in patients with mCRPC.*
- *To estimate efficacy of PF 06952229 in combination with enzalutamide at the estimated RP2D in patients with mCRPC.*
- *To confirm the RP2D of PF 06952229 in combination with enzalutamide in patients with mCRPC.*

Secondary Objectives

- *To estimate additional efficacy of PF 06952229 at the estimated RP2D in patients with mCRPC.*
- *To further evaluate the PK of PF 06952229 when given in combination with enzalutamide.*
- *To evaluate immune cells in paired pre and post treatment tumor biopsies (where available).*

CCI [REDACTED]

2.2. Study Design

This is a Phase 1, open label, multi center, multiple dose, dose-escalation and expansion, safety, tolerability, PK, CCI [REDACTED] study of PF-06952229 in previously treated patients with advanced or metastatic cancers that may have high TGF β signatures and EMT expression.

The study includes Parts 1A and 1B, which are dose-escalation cohorts, and Parts 2A and 2B, which are dose expansion cohorts. The primary objectives for Part 1A are to assess the safety and tolerability of PF-06952229 administered as a single agent and to determine maximum tolerated dose (MTD). The primary objectives for Part 1B are to assess the safety and tolerability of PF-06952229 administered with enzalutamide and to determine MTD. The primary objectives for Part 2A are to confirm PF-06952229 safety and tolerability, estimate the single agent efficacy of PF-06952229 and determine a recommended Phase 2 dose (RP2D). The primary objectives of Part 2B are to confirm the safety profile of PF-06952229 combined with enzalutamide, estimate the efficacy of PF-06952229 combined with enzalutamide and determine a RP2D for the combination.

Part 1A is a sequential single-agent dose-escalation conducted in patients with advanced or metastatic solid tumors who have failed standard of care treatment or for whom no standard of care exists. Successive cohorts of patients are to receive escalating doses of PF-06952229 on an outpatient basis starting from 20 mg BID, which is based on non-clinical data. Nine candidate dose levels are planned using an Accelerated Titration Design (ATD) until reaching 250 mg BID, after which the design will revert to modified target probability interval (mTPI). The highest tested dose will not exceed 800 mg BID. If an MTD is not

observed during the 28 day safety window, additional dose levels may be considered based on PK, safety, tolerability, CCI [REDACTED] assessments. Based on PK and safety, additional patients can be added to a dose lower than the MTD and also may be moved forward to monotherapy expansion.

[figure not shown]
Part 1B is a dose-escalation of PF-06952229 in the combination of enzalutamide conducted in patients who were previously treated with metastatic castration-resistant prostate cancer (mCRPC). The starting dose of PF-06952229 will be the MTD or maximum administered dose (MAD) of Part 1A. Based on evolving PK, CCI [REDACTED] and safety profiles, assessed in Part 1A, Part 1B may commence before reaching the MTD, and will follow an mTPI design. The maximum PF-06952229 dose for the combination escalation may be higher than the monotherapy MTD due to the potential DDI between enzalutamide and PF-06952229, but not higher than 800 mg BID.

Part 2A and Part 2B are expansion cohorts for monotherapy and combination therapy, respectively, in patients with previously treated mCRPC.

To assess baseline TGF β related biomarker signatures that may correlate with clinical efficacy, all patients enrolled in Part 1 will be required to provide a recent archival tumor sample or to undergo a fresh pre treatment biopsy if archival samples are unavailable prior to trial treatment.

Part 2 patients are required to provide either a recent archival tumor biopsy or, for all patients in Part 2A and from approximately 10 patients in Part 2B, mandatory de novo biopsies. Mandatory de novo pre-treatment and on-treatment tumor biopsies may not be required where it is determined that it is not medically feasible (such as constituting unacceptable medical risks). However, this would require agreement of Investigator and Sponsor.

See [Figure 1](#) for the study schema.

Figure 1. Study Schema

All patients:

1. Will undergo up to 4 weeks of screening prior to study entry, ie, Cycle 1 Day 1.
2. Will receive doses of PF 06952229, administered orally on 28 day cycle, 7 days on, 7 days off, up to 2 years. Any additional treatment with PF 06952229 beyond 2 years shall be discussed and approved by the Sponsor.
3. Treatment with investigational product (IP) will continue until disease progression, patient refusal, or unacceptable toxicity occurs, whichever occurs first. However, patients who demonstrate clinical benefit (despite radiographic progression) with manageable toxicity and are willing to continue receiving the investigational product will be given the opportunity to continue treatment upon agreement between investigator and sponsor.
4. Will undergo a follow up visit approximately 4 weeks after the last dose for AE and serious adverse event (SAE) collection.

The proposed doses, schedule(s), and PK CCI time points may be reconsidered and amended during the study based on the emerging safety and PK CCI data.

3. ENDPOINTS AND COVARIATES: DEFINITIONS AND CONVENTIONS

3.1. Primary Endpoint(s)

Part 1

- *First cycle Dose Limiting Toxicities (DLTs). The specific definition of DLT is provided in the study protocol.*
- *Adverse events (as graded by National Cancer Institute Common Terminology Criteria for Adverse Events version 5.0).*

Part 2

- *First cycle Dose Limiting Toxicities (DLTs) in combination with enzalutamide for CRPC and palbo/letrozole for HR+ BC.*
- *Adverse Events as characterized by type, frequency, severity (as graded by National Cancer Institute Common Terminology Criteria for Adverse Events (NCI CTCAE version 5.0), timing, seriousness, and relationship to study therapy.*
- *Laboratory abnormalities as characterized by type, frequency, severity (as graded by NCI CTCAE version 5.0), and timing.*

3.2. Secondary Endpoint(s)

Parts 1 and 2

- *Pharmacokinetic parameters of PF-06952229.*
- *Single Dose (SD) C_{max} , T_{max} , AUC_{last} , and as data permit, AUC_{inf} , CL/F , V_z/F , and $t_{1/2}$.*
- *Multiple Dose (MD) $C_{ss,max}$, $T_{ss,max}$, AUC_{last} , $C_{ss,min}$, and as data permit CL_{ss}/F , V_{ss}/F , $t_{1/2}$, and R_{ac} (AUC_{last}/AUC_{last}).*
- *Objective Response Rate (ORR). PSA50 Response Rate for prostate cancer patients only.*
- *Time to event endpoints (Duration of Response (DOR), Progression Free Survival (PFS), Overall Survival (OS), Time to Progression (TTP), Time to Response (TTR).*
- *For prostate cancer patients, response assessment will be based on Prostate Cancer Response criteria (PCWG2). For other tumor types, response will be assessed using the Response Evaluation Criteria in Solid Tumors (RECIST 1.1).*

Horizontal bar chart showing CCI values for 15 categories. The categories are listed on the y-axis, and the x-axis represents the CCI value from 0 to 100. The bars are dark gray, and the y-axis labels are rotated 90 degrees.

Category	CCI
CCI	85
Category 1	15
Category 2	35
Category 3	75
Category 4	95
Category 5	98
Category 6	100
Category 7	100
Category 8	100
Category 9	100
Category 10	100
Category 11	100
Category 12	100
Category 13	100
Category 14	100
Category 15	100

3.4. Covariates

Biomarker data may be considered as covariates in PK and anti-tumor efficacy exploratory analyses. Covariates may also be considered when exploring QTc and PK relationship.

4. ANALYSIS SETS

4.1. Full Analysis Set

The full analysis set includes all enrolled patients. This is equivalent to the ITT (intent-to-treat) population.

4.2. Safety Analysis Set

The safety analysis set includes all enrolled patients who receive at least one dose of study treatment.

4.3. 'PER PROTOCOL' Analysis Set (evaluable for MTD)

The per protocol analysis set includes all enrolled patients who receive at least one dose of study treatment and who do not have major treatment deviations during the first cycle.

Patients with major treatment deviations during the first cycle of treatment are not evaluable for the MTD assessment and will be replaced as needed to permit the MTD estimation.

Major treatment deviations include the failure to satisfy major entry criteria (eg, confirmation of the target disease; signed informed consent) or use of other anticancer treatments during the active treatment period and disease follow up phases other than as defined/allowed in this protocol. Major treatment deviations will also include:

- *Administration of less than 70% of the planned number of doses of PF-06952229 (provided that the reduction in doses is not due to toxicity attributable to PF-06952229).*
- *Administration of more than 110% of the planned number of doses of PF-06952229.*

4.4. Modified Intent to Treat (mITT) Population

The modified intent to treat (mITT) is the analysis population that will follow the ITT principle and include patients receiving at least 1 dose of investigational product with baseline assessment and at least 1 post baseline assessment, disease progression, or death before the first tumor assessment. The mITT population will be used for analyses and to support conference presentations when the study is still ongoing.

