9.6. Sample Size Determination

9.6.1. Part 1

In Part 1, patients will participate in a dose escalation phase aimed at estimating the MTD. The sample size for this component of the study will vary depending on the number of DLTs observed.

A maximum of 60 patients are expected to be enrolled in the dose escalation safety cohorts in Part 1, including approximately 40 patients for the monotherapy dose escalation and approximately 20 patients for the combination dose escalation. The actual number of patients enrolled will depend on the tolerability of PF-06952229 and the number of dose levels required to identify the MTD/RP2D. It is expected that the dose escalation process can be stopped and MTD declared with approximately 6 to 12 patients at the MTD dose. As for the number of patients treated at each dose, it is expected to be at 1 to 4 patients for the doses actually studied. However, since variable cohort size is allowed, the actual number of patients treated at each dose (including MTD) will vary from 1 to 12 patients.

9.6.2. Part 2

For PF-06952229 single agent expansion in patients with mCRPC, the planned sample size of the expansion cohort is 10 based on clinical consideration.

PF-06952229 single agent in combination with enzalutamide for patients with metastatic castration-resistant prostate cancer (mCRPC), assuming a sample size of 20, and the observed PSA50 response is 60% (12/20), the Bayesian posterior probability to demonstrate that the "True PSA50 response" is greater than 37% is 98.15%. Assuming 80% of the 20 patients have measurable disease and are response evaluable (16 patients evaluable), and the observed ORR is 43.75% (7/16), the Bayesian posterior probability to demonstrate that the "True ORR" is greater than 30% is 86.89%.

All the Bayesian calculations above assume a non-informative Uniform (0,1) prior

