5.1. Statistical Hypotheses

There are no statistical hypotheses.

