5.2.3. Sample Size Determination

Part 1

In Part 1, patients will participate in a dose escalation phase aimed at estimating the MTD. The sample size for this component of the study will vary depending on the number of DLTs observed.

A maximum of 60 patients are expected to be enrolled in the dose escalation safety cohorts in Part 1, including approximately 40 patients for the monotherapy dose escalation and approximately 20 patients for the combination dose escalation. The actual number of patients enrolled will depend on the tolerability of PF 06952229 and the number of dose levels required to identify the MTD/RP2D. It is expected that the dose escalation process can be stopped and MTD declared with approximately 6 to 12 patients at the MTD dose. As for the number of patients treated at each dose, it is expected to be at 1 to 4 patients for the doses actually studied. However, since variable cohort size is allowed, the actual number of patients treated at each dose (including MTD) will vary from 1 to 12 patients.

Part 2

For PF 06952229 single agent expansion in patients with mCRPC, the planned sample size of the expansion cohort is 10 based on clinical consideration.

PF 06952229 single agent in combination with enzalutamide for patients with metastatic castration resistant prostate cancer (mCRPC), assuming a sample size of 20, and the observed PSA50 response is 60% (12/20), the Bayesian posterior probability to demonstrate that the "True PSA50 response" is greater than 37% is 98.15%. Assuming 80% of the 20 patients have measurable disease and are response evaluable (16 patients evaluable), and

the observed ORR is 43.75% (7/16), the Bayesian posterior probability to demonstrate that the "True ORR" is greater than 30% is 86.89%.

All the Bayesian calculations above assume a non informative Uniform (0,1) prior.

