6.3. Analysis for Secondary Endpoints

6.3.1. Efficacy Endpoints Analysis

ORR, as assessed using PCWG2 for prostate cancer and RECIST version 1.1 for other tumor types, is a key efficacy endpoint. The following analyses will be performed in the mITT population by tumor type and pooled:

The ORR, along with other efficacy analyses will be performed in the mITT population. Part 1 and Part 2 data will be summarized separately, and may also be pooled together for analysis if deemed necessary. Specifically, the key tables in Part 2 include:

1. ORR by visit: investigator provided tumor response CR, PR, and CR+PR will be presented by descriptive statistics (frequency and percentage) and 95% confidence interval.
2. Best overall response of CR, PR, and CR+PR. This will include best overall response derivation without confirmation and with confirmation. Descriptive statistics (frequency and percentage) and 95% confidence interval will be provided.

Tumor response data in Part 1, Part 2 and across the two Parts may be summarized with descriptive statistics (frequency and percentage) in the following groups by visit and then best overall response across all visits:

- Overall summary for all doses and all tumor types;
- By tumor type regardless of dose;
- By dose regardless of tumor type;
- By dose and tumor type if data permit.

Summary tables of best overall response rate, PFS, OS, DOSD, and DOR may be provided by the groups aforementioned when deemed necessary (eg, if there are ≥ 5 patients in a specific group).

In addition, PSA50 Response Rate defined as $\geq 50\%$ PSA reduction from baseline assessed by PCWG2 for prostate cancer patients will be summarized similarly as ORR. See [Section 9.5](#) for more details on PSA measurement.

Efficacy listings (tumor measurements listings and tumor response listings) will be provided that include the investigator provided tumor measurement data, tumor response, best overall response, first CR/PR date, last date with CR or PR, most recent date without progression, progression date, death date, and last tumor assessment date, etc.

Endpoint	Analysis Set	Statistical Method	Model/Covariates/Strata	Missing Data
Overall response	mITT	Exact CI	See aforementioned summary descriptions on data pooling across dose and tumor type	Observed case
Overall Survival	ITT	Kaplan-Meier	See aforementioned summary descriptions on data pooling across dose and tumor type	Censored at last visit

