Confirmatory Imaging Requirements for Patients With CRPC Based on RECIST v1.1 and PCWG2

Disease Site	Response	Progression ^[1]
Soft tissue	Must be confirmed at least 4 weeks later	No confirmation required
Bone	Not applicable	Must be confirmed at least 6 weeks later

[1] To inform permanent treatment discontinuation.

Objective Response Status at Each Evaluation

Target Lesions	Non-target Disease	New Lesions	Objective status
CR	CR	No	CR
CR	Non-CR/Non-PD	No	PR
CR	Indeterminate or Missing	No	PR
PR	Non-CR/Non-PD, Indeterminate, or Missing	No	PR
SD	Non-CR/Non-PD, Indeterminate, or Missing	No	Stable
Indeterminate or Missing	Non-PD	No	Indeterminate
PD	Any	Yes or No, including bone determination	PD
Any	PD	Yes or No	PD
Any	Any	Yes	PD

If there is a protocol deviation and a patient has been enrolled allows enrollment of patients with only non-target disease, the following table will be used:

Objective Response Status at Each Evaluation for Patients With Non-Target Disease Only

Non-target Disease	New Lesions	Objective status
CR	No	CR
Non-CR/Non-PD	No	Non-CR/Non-PD
Indeterminate	No	Indeterminate
Unequivocal progression	Yes or No	PD
Any	Yes	PD

Procedures for Assessing PSA Response/Progression Post Study Treatment

PSA measurements will be performed on C1D1 (± 14 days) and Day 1 of Cycle 4, 7, 10 and every third cycle thereafter, as well as at the End of Treatment visit. Increases and decreases will be tracked in order to assess disease response. The PSA readings on its own will not be used to define progression in this protocol. PSA response and PSA progression will be defined according to the consensus guidelines of the PCWG2:

- PSA partial response is defined as a $\geq 50\%$ decline in PSA from Cycle 1 Day 1 (baseline) PSA value. This PSA decline must be confirmed to be sustained by a second PSA value obtained 4 or more weeks later.
- PSA progression date is defined as the date that a $\geq 25\%$ increase and an absolute increase of ≥ 2 ng/mL above the nadir is documented, which is confirmed by a second consecutive value obtained 4 or more weeks later. The first PSA reading will be obtained at week 12.

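### PSA50 and ORR are analysed in an mITT, observed-case set that can lose some treated patients with no recorded response, which could bias the Part 2 response rates upward

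*SAP*

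**What the plan says.** SAP 4.4 (same definition in Protocol 9.1) admits to mITT a patient who received at least one dose, has a baseline assessment, and has "at least 1 post baseline assessment, disease progression, or death before the first tumor assessment". It describes the set as following the ITT principle and intends it also for conference presentations while the study is running. It does not say whether an assessment means a scan, a PSA or either.

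SAP 6.3.1 places ORR and the other efficacy analyses in mITT. Its table gives overall response an exact confidence interval and the missing-data entry "Observed case", which is not defined. PSA50 has no row of its own; it "for prostate cancer patients will be summarized similarly as ORR". Of the tabled endpoints, only overall survival uses the ITT set. No ORR or PSA50 analysis in all treated patients is planned, and no rule counts patients without data as non-responders.

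On timing, SAP 9.5 states: "The first PSA reading will be obtained at week 12". That is Cycle 4 Day 1, and an End of Treatment PSA is also scheduled.

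On planning, Protocol 9.6.2 sizes Part 2B PSA50 "assuming a sample size of 20, and the observed PSA50 response is 60% (12/20"). ORR is planned with "80% of the 20 patients have measurable disease and are response evaluable (16 patients evaluable"), of whom 7 respond. Part 2A has 10 patients on clinical grounds, with no response calculation.

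**The concern.** PSA50 is a primary endpoint of Parts 2A and 2B in Protocol section 2, although SAP 3.2 lists it as secondary. Its denominator depends partly on what happens after treatment starts. A patient who stops early for toxicity or withdraws, and is never assessed again, has had no recorded benefit and would usually count as a non-responder. Under SAP 4.4 that patient is removed.

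Symptomatic decline does not bring the patient back in. Protocol Appendix 6 and SAP 9.4 both say that stopping for global deterioration without objective evidence is not recorded as progression.

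PSA50 has a second exposure. A Week 8 scan, progression or early death keeps a patient in mITT before any Week 12 PSA exists. The plan does not say whether the observed-case rule then counts that patient as a non-responder or leaves him out. Two analysts could report different PSA50 rates from the same data. In cohorts of 10 and 20, one or two patients visibly move the rate.

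**Working it through.** **Inputs.** Part 2B: n = 20 and 12 responders in the planning case (Protocol 9.6.2, SAP 5.2.3). Threshold 37%, Uniform(0,1) prior (SAP 5.2.3). Number of excluded treated patients k: not in the documents, so k = 0 to 4 is assumed, each counted as a non-responder in the all-treated analysis.

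**Reproducing the plan's figure.** With r responders among n and a uniform prior, the posterior is Beta(1 + r, 1 + n − r). For 12/20, P(p > 0.37) under Beta(13, 9) is 98.21%. The plan says that the true rate "is greater than 37% is 98.15" per cent, a gap of 0.06 points. Beta(12, 8), with no prior counts, gives 98.15% exactly. The gap is immaterial for PSA50. The ORR figure departs more (89.54% under the uniform prior against 86.89% stated), which is a separate matter.

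**Effect of exclusions.** The reported rate is r/(20 − k), the all-treated rate is r/20, and the difference is rk/[20(20 − k)]. For r = 10 and k = 1 this is 10/380 = 2.6 points; for r = 10 and k = 2 it is 20/360 = 5.6 points.

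| k | r = 9: rate (posterior) | r = 10: rate (posterior) | r = 12: rate (posterior) |
|---|---|---|---|
| 0 | 45.0% (0.7848) | 50.0% (0.8901) | 60.0% (0.9821) |
| 1 | 47.4% (0.8350) | 52.6% (0.9225) | 63.2% (0.9898) |
| 2 | 50.0% (0.8787) | 55.6% (0.9482) | 66.7% (0.9946) |
| 3 | 52.9% (0.9153) | 58.8% (0.9675) | 70.6% (0.9974) |
| 4 | 56.3% (0.9443) | 62.5% (0.9811) | 75.0% (0.9989) |

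Read the other way, a reported 11/18 = 61.1% has posterior 0.9815, level with the planning figure, but is 11/20 = 55.0% of treated patients (0.9519).

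**Other endpoints, for scale only.** In Part 2A, 3/10 = 30.0% becomes 3/9 = 33.3% with one exclusion. For ORR, the planned 7/16 = 43.75% would be 7/17 = 41.2% if one further treated patient with measurable disease had been left out as not evaluable.

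**The case against.** The strongest reply is that few patients can fall through.

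- The mITT definition keeps progression and early death. A reader might infer that every treated patient without a post-baseline assessment is dropped; the sentence itself rules that out.
- Protocol 7.8 continues scans after treatment stops, until new systemic therapy or permanent loss to radiographic follow-up. Protocol 6.4 keeps patients who stop treatment in follow-up. An End of Treatment visit, with PSA and CT/MRI, is due within 4 weeks of the last dose. Stopping for toxicity does not by itself remove anyone.
- The observed-case entry is undefined. The worked ORR example in SAP section 6 equates the denominator with the population set and keeps unconfirmed responders in it.
- A reader might infer that all Part 2 rates depart from a 12/20 basis. They do not. ORR was planned on 16 measurable, evaluable patients, and Part 2A has no response planning basis.
- SAP 5.1 says "There are no statistical hypotheses". The 37% posterior appears only in the sample-size text, with no decision rule attached. The exact 95% interval for 12/20 runs from 36.1% to 80.9%, so a shift of a few points is small against the precision.
- Exclusions will be visible, because SAP 6.1 accounts for patients on the full analysis set and responses are listed individually.

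Most of this stands and limits the size. It does not close the gap. The End of Treatment footnote in the Part 2 schedules excuses disease assessments already done within the previous 8 or 12 weeks, so a patient who stops in the first weeks may have no new scan, and possibly no new PSA if PSA counts as a disease assessment. Patients can also refuse further visits. An undefined rule for a primary endpoint's denominator is itself a defect, and wide intervals do not justify a one-directional bias.

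**Conclusion.** The concern holds in limited form. As written, the rule can remove treated patients with no recorded response and cannot work in the other direction, so PSA50 and ORR could be biased upward. Only for Part 2B PSA50 is this also a departure from the planning denominator.

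The size rests on an assumed number of exclusions. With none there is no bias. With one or two, a true 10/20 would be reported about 3 or 6 points higher, and the posterior probability of exceeding 37% would rise from 0.89 to 0.92 or 0.95. A reader might conclude that the rates will be inflated or that a development decision would change. The documents support neither: they give no dropout or non-evaluable rate, and no decision depends on the posterior. The change is still worth making because PSA50 is a protocol primary endpoint and the cohorts are small.

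**What to change.** In SAP 6.3.1, make the main Part 2 analyses PSA50 in all treated patients with a baseline PSA, and ORR in all treated patients with measurable disease at baseline. Count patients with no post-baseline value as non-responders in both. Keep the mITT observed-case results as a sensitivity analysis, and for these say what counts as an assessment and what the observed-case rule does with an mITT patient who has no PSA. Report the number excluded, with reasons, beside each rate. Fix this before any ongoing-study presentation of response.

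The cost is SAP wording and a slightly lower reported rate. Protocol 9.3 names no analysis set for PSA50, so the SAP is the natural place. The sponsor should check whether the clause in Protocol section 9 on major changes to primary endpoint analyses also calls for an amendment.
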